Official Title: A PHASE III, OPEN-LABEL, MULTICENTER, TWO-ARM, RANDOMIZED STUDY TO INVESTIGATE THE EFFICACY AND SAFETY OF COBIMETINIB PLUS ATEZOLIZUMAB VERSUS PEMBROLIZUMAB IN PATIENTS WITH PREVIOUSLY UNTREATED ADVANCED *BRAF*^{V600} WILD-TYPE MELANOMA

NCT Number: NCT03273153

Document Date: SAP Version 3: 03 February 2020

STATISTICAL ANALYSIS PLAN

TITLE: A PHASE III, OPEN-LABEL, MULTICENTER, TWO-ARM, RANDOMIZED STUDY TO INVESTIGATE THE EFFICACY AND SAFETY OF COBIMETINIB PLUS ATEZOLIZUMAB VERSUS PEMBROLIZUMAB IN PATIENTS WITH PREVIOUSLY UNTREATED ADVANCED *BRAF*^{V600} WILD-TYPE MELANOMA

PROTOCOL NUMBER: CO39722

STUDY DRUG: Cobimetinib and Atezolizumab

VERSION NUMBER: 3

IND NUMBER: 135,717

EUDRACT NUMBER: 2016-004387-18

SPONSOR: F. Hoffmann-La Roche Ltd

PLAN PREPARED BY: [REDACTED], M.Math.

DATE FINAL: Version 1: 02 November 2018
Version 2: 16 May 2019

DATE AMENDED: Version 3: See electronic date stamp below

STATISTICAL ANALYSIS PLAN APPROVAL

Date and Time(UTC)	Reason for Signing	Name
03-Feb-2020 12:37:52	Company Signatory	[REDACTED]

CONFIDENTIAL

This is an F. Hoffmann-La Roche Ltd document that contains confidential information. Nothing herein is to be disclosed without written consent from F. Hoffmann-La Roche Ltd.

STATISTICAL ANALYSIS PLAN, VERSION 2

RATIONALE FOR AMENDMENT

A change has been made in Section 4.4 (“Efficacy Analyses”) to address the potential risk of over-stratification in efficacy analyses.

The stratification factors will be those used for randomization and will be obtained from the IWRS (PD-L1 status, baseline serum LDH level and geographic region). Due to the potential risk of over-stratification (Akazawa et al. 1997), if at least one stratum (i.e., a combination of stratification factor levels across PD-L1 status, baseline serum LDH level and geographic region) has fewer than 10 IRC-assessed PFS events across treatment arms, the stratification factor (one of three stratification factors: PD-L1 status, baseline serum LDH level and geographic region per IWRS) which contains the level with the smallest number of patients will be removed from the stratified analyses. The removal of the stratification factors will continue until there is no stratum with fewer than 10 IRC-assessed PFS events. The final set of stratification factors used in stratified analyses will be applied to all endpoints where stratified analyses are planned.

STATISTICAL ANALYSIS PLAN, VERSION 3

RATIONALE FOR AMENDMENT

---------	---	----

LIST OF FIGURES

Figure 1	Study Schema.....	8
----------	-------------------	---

LIST OF APPENDICES

Appendix 1	Protocol Synopsis	24
Appendix 2	Schedule of Assessments.....	37
Appendix 3	Schedule of Pharmacokinetic, Immunogenicity, and Biomarker Samples.....	48
Appendix 4	Response Evaluation Criteria in Solid Tumors, Version 1.1.....	49

1. **BACKGROUND**

This Statistical Analysis Plan (SAP) provides details of the planned analyses and statistical methods for Study CO39722 (IMspire170): A Phase III, open-label, multicenter, two-arm, randomized study to investigate the efficacy and safety of cobimetinib plus atezolizumab versus pembrolizumab in patients with previously untreated advanced *BRAF*^{V600} wild-type melanoma. The background for the study can be found in the study protocol.

It is anticipated that positive results from Study CO39722 will support the submission of filing applications globally for the use of cobimetinib plus atezolizumab for the treatment of patients with previously untreated advanced *BRAF*^{V600} wild-type melanoma. For purposes of registration, the analyses outlined in this SAP will supersede those specified in the protocol.

2. **STUDY DESIGN**

[figure not shown]
Study CO39722 is a Phase III, multicenter, open-label, randomized study designed to evaluate the efficacy, safety, and pharmacokinetics of cobimetinib plus atezolizumab compared with pembrolizumab in treatment-naive patients with advanced *BRAF*^{V600} wild-type melanoma.

This study will be conducted globally and approximately 450 patients will be randomized in a 1:1 ratio to one of two treatment arms:

- Arm A: Patients will receive 60 mg of cobimetinib by mouth (PO) on a 21 days on, 7 days off (21/7) schedule (dosing on Days 1-21, followed by no dosing on Days 22-28) plus 840 mg of atezolizumab by intravenous (IV) infusion on Days 1 and 15 of each 28-day cycle (n=225).
- Arm B: Patients will receive 200 mg of pembrolizumab administered by IV infusion every 3 weeks (Q3W) (n=225).

The study schema is presented in [Figure 1](#).

Figure 1 Study Schema

PD=progressive disease; PD-L1=programmed death–ligand 1; Q3W=every 3 weeks; Q2W=every 2 weeks, R=randomization; RECIST v1.1=Response Evaluation Criteria in Solid Tumors, Version 1.1; 21/7=21 days on/7 days off (schedule).

Stratification factors are PD-L1 (programmed death-ligand 1) status (IC0 [tumor-infiltrating immune cell 0] vs. IC1, 2, 3), baseline serum LDH (lactate dehydrogenase) level (less than or equal to the upper limit of normal [ULN] vs. greater than the ULN), and geographic region (North America vs. Europe vs. Australia, New Zealand, and others).

A permuted-block randomization will be applied to ensure a balanced assignment to each treatment arm. Randomization and stratification will be managed through an interactive Web-based response system (IWRS).

All eligible patients will be randomized to treatment in a 1:1 ratio to either Arm A (cobimetinib plus atezolizumab) or Arm B (pembrolizumab).

All patients will be closely monitored for safety and tolerability during all cycles of therapy, at the treatment discontinuation visit, and during the follow-up period. The National Cancer Institute Common Terminology Criteria for Adverse Events, Version 4.0 (NCI CTCAE v4.0) will be used to characterize the toxicity profile of study treatments for all patients. Patients will be assessed for adverse events (AEs) according to the schedule of activities (see [Appendix 2](#)) and as necessary throughout the study.

Tumor response will be evaluated according to Response Evaluation Criteria in Solid Tumors, Version 1.1 (RECIST v1.1) (see [Appendix 4](#)). Any evaluable and measurable disease must be documented at screening and re-assessed at each subsequent tumor evaluation. Investigators will assess tumor response at 8-week intervals, regardless of any dose delays or treatment cycle.

Study treatment will continue for all patients until investigator-determined disease progression according to RECIST v1.1 that is confirmed by repeat scans 4-8 weeks later, unacceptable toxicity, death, patient or physician decision to withdraw, or pregnancy, whichever occurs first. Patients who experience disease progression must have scans repeated 4-8 weeks after initial documentation of progression to confirm disease progression. These results will be used as part of the exploratory analyses for assessing efficacy based on immune-modified RECIST. Tumor assessments are to continue according to schedule for patients who discontinue treatment for reasons other than confirmed disease progression. Clinically stable patients who have disease progression may continue study treatment, as described in protocol Section 3.1.1. After treatment discontinuation, patients will be followed for disease progression if applicable and followed for survival until death, withdrawal of consent, or loss to follow-up, whichever occurs first. If a patient withdraws from the study, study staff may use a public information source (e.g., county records) to obtain information about survival status only.

The primary endpoint is Independent Review Committee (IRC)-assessed Progression-Free Survival (PFS) per RECIST v1.1, defined as the time from randomization to the first occurrence of disease progression, as determined by an IRC according to RECIST v1.1, or death from any cause, whichever occurs first. The analysis of the primary endpoint of PFS will occur after a total of approximately 240 events have occurred.

2.1 PROTOCOL SYNOPSIS

The Protocol Synopsis is in [Appendix 1](#). For additional details, see the Schedule of Assessments in [Appendix 2](#). For schedule of pharmacokinetic, immunogenicity, and biomarker sample, see [Appendix 3](#).

2.2 ENDPOINTS

2.2.1 Primary Efficacy Endpoint

The primary efficacy endpoint is IRC-assessed PFS per RECIST v1.1, defined as the time from randomization to the first occurrence of disease progression, as determined by an IRC according to RECIST v1.1, or death from any cause, whichever occurs first.

2.2.2 Secondary Efficacy Endpoints

- Overall Survival (OS), defined as the time from randomization to death from any cause
- Two-year landmark survival, defined as survival at 2 years
- Objective response, defined as a complete response or a partial response on two consecutive occasions ≥ 4 weeks apart, as determined by the IRC according to RECIST v1.1

- Objective response, defined as a complete response or a partial response on two consecutive occasions ≥ 4 weeks apart, as determined by the investigator through use of RECIST v1.1
- PFS, defined as the time from randomization to the first occurrence of disease progression, as determined by the investigator through use of RECIST v1.1, or death from any cause, whichever occurs first
- Disease control Rate (DCR), defined as a complete response, a partial response, or stable disease at 16 weeks, as determined by the IRC through use of RECIST v1.1
- DCR, defined as a complete response, a partial response, or stable disease at 16 weeks, as determined by the investigator through the use of RECIST v1.1
- Duration of objective response, defined as the time from the first occurrence of a documented objective response to disease progression, as determined by the IRC through use of RECIST v1.1, or death from any cause, whichever occurs first
- Duration of objective response, defined as the time from the first occurrence of a documented objective response to disease progression, as determined by the investigator through use of RECIST v1.1, or death from any cause, whichever occurs first
- The change from baseline in Health-Related Quality of Life (HRQoL) scores, as assessed through use of the two-item Global Health Status/Quality of Life (GHS/QoL) subscale of the European Organization for Research and Treatment of Cancer Quality of Life Core 30 (EORTC QLQ-C30) questionnaire, at specified timepoints while receiving treatment

2.2.3 Exploratory Efficacy Endpoints

- Objective response according to investigator-assessed immune-modified RECIST
- Duration of response rate (DOR) according to investigator-assessed immune-modified RECIST
- PFS according to investigator-assessed immune-modified RECIST
- Change from baseline in HRQoL, functioning and commonly reported symptoms (insomnia, pain, and fatigue), as assessed through use of the EORTC QLQ-C30 GHS, functioning and symptom scales, at specified timepoints, including progression, treatment discontinuation and post-study treatment
- The number and proportion of patients who improve, remained stable, and worsen from baseline as measured by the EORTC QLQ-C30, GHS, functioning, and symptom scales, at specified timepoints, including progression, treatment discontinuation and post-study treatment

2.2.4 Pharmacokinetic Endpoints

- Plasma concentration of cobimetinib at specified timepoints
- Serum concentration of atezolizumab at specified timepoints

2.2.5 Safety Endpoints

- Occurrence and severity of AEs, with severity determined through use of NCI CTCAE v4.0
- Change from baseline in selected vital signs
- Change from baseline in selected clinical laboratory test results

2.2.6 Immunogenicity Endpoint

- Incidence of anti-drug antibodies (ADAs) during the study relative to the prevalence of ADAs at baseline

Exploratory analysis investigating the relationship between ADA status and efficacy, safety, or PK endpoints will be performed.

2.2.7 Exploratory Biomarker Endpoint

- Relationship of immune contextures, such as PD-L1, cluster of differentiation 8 (CD8)-positive T cells, or major histocompatibility complex expression, as identified by immunohistochemistry and gene signature profiling, genetic alterations, such as *RAS* and *NF1*, with efficacy, pharmacokinetics, immunogenicity, or other biomarker endpoints.

2.2.8 Exploratory Health Utility Objective

- Health status utility score based on the European Quality of Life 5-Dimension, 5-Level (EQ-5D-5L) questionnaire

2.3 DETERMINATION OF SAMPLE SIZE

Approximately 450 patients will be randomized into the study.

The overall type I error (α) for this study is 0.05 (two-sided). Formal treatment comparisons will be performed by first evaluating the primary endpoint of IRC-assessed PFS (per RECIST v1.1) at $\alpha=0.01$ (two-sided). If PFS is statistically significant at $\alpha=0.01$, then the key secondary endpoints will be evaluated at $\alpha=0.05$ (two-sided) in a hierarchical manner in the following order: OS, IRC-assessed objective response rate (ORR), and landmark OS. IRC-assessed ORR and landmark OS will be tested when OS crosses the pre-specified boundary.

The type I error (α) for the analysis of the primary endpoint of IRC-assessed PFS is 0.01 (two-sided). The analysis of the primary endpoint of IRC-assessed PFS will take place when approximately 240 PFS events have occurred. Statistical considerations are based on the following assumptions:

- Stratified log-rank test at 0.01 significance level (two-sided)
- Median PFS of 5.5 months for the pembrolizumab arm
- Median PFS of 10.0 months for the cobimetinib plus atezolizumab arm
- Enrollment period of approximately 12 months
- Annual dropout rate of 5%
- No interim analysis for PFS

A total of 240 PFS events provides approximately 98% power to detect an improvement in median PFS from 5.5 months in the pembrolizumab arm to 10.0 months in the cobimetinib plus atezolizumab arm. This corresponds to a hazard ratio (HR) of 0.55, with a minimal detectable difference of 0.72. The PFS analysis will be conducted approximately 17 months after first patient in (FPI). The final analysis of the secondary endpoint of OS will be performed after the occurrence of approximately 295 deaths. A total of 295 deaths provides approximately 60% power to detect an improvement in median OS from 28 months in the pembrolizumab arm to 37.5 months in the cobimetinib plus atezolizumab arm, corresponding to an HR of 0.75, or 80% power to detect an HR of 0.70. Two interim analyses of OS will be conducted. The final OS analysis will be conducted approximately 68 months after FPI.

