The final analysis of the secondary endpoint of OS will be performed after the occurrence of approximately 295 deaths. A total of 295 deaths provides approximately 60% power to detect an improvement in median OS from 28 months in the pembrolizumab arm to 37.5 months in the cobimetinib plus atezolizumab arm, corresponding to an HR of 0.75, or 80% power to detect an HR of 0.70. Two interim analyses of OS will be conducted. The final OS analysis will be conducted approximately 68 months after FPI.

Interim Analyses

No interim analyses of the primary endpoint of PFS will be performed.

Interim Efficacy Analyses of the Secondary Efficacy Endpoint

The study will incorporate three OS analyses (two interim analyses and one final analysis). The first overall survival (OS) interim analysis will be performed at the time of the primary PFS analysis when a projected number of 80 deaths are expected to have occurred. The second OS interim analysis will be performed after the occurrence of approximately 153 deaths and is projected to occur at approximately 28 months after the first patient is randomized. The final OS analysis will be performed after the occurrence of approximately 295 deaths and is projected to occur approximately 68 months after the first patient is randomized. Generalized Haybittle-Peto boundaries with unequal p-values will be used to control the overall type I error of the OS comparison at a two-sided 0.05 significance level.

LIST OF ABBREVIATIONS AND DEFINITIONS OF TERMS

Abbreviation	Definition
ADA	anti-drug antibody; also known as anti-therapeutic antibody (ATA)
APC	antigen-presenting cell
CI	confidence interval
CPK	creatine phosphokinase
CRC	colorectal cancer
CRS	cytokine-release syndrome
CT	computed tomography
CTCAE	Common Terminology Criteria for Adverse Events
ctDNA	circulating-tumor DNA
CTLA-4	cytotoxic T lymphocyte-associated protein-4
DCR	disease control rate
DOR	duration of response
EC	Ethics Committee
ECG	Electrocardiogram
ECHO	Echocardiogram
eCRF	electronic Case Report Form
EDC	electronic data capture
EQ-5D-5L	European Quality of Life 5-Dimension, 5-Level questionnaire
EDC	electronic data capture
EORTC QLQ-C30	European Organisation for Research and Treatment of Cancer Quality of Life Questionnaire Core 30
EU	European Union
FDA	(U.S.) Food and Drug Administration
FFPE	formalin-fixed, paraffin-embedded
FPI	first patient in
GHS	global health status
HBcAb	hepatitis B core antibody
HbsAg	hepatitis B surface antigen

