PFS. Furthermore, the secondary endpoints of OS, 2-year landmark OS, and IRC-assessed ORR and DOR will provide additional information for patients and physicians that is unaffected by knowledge of treatment assignment.

3.3.9 Rationale for Selection of Primary Endpoint: Progression-Free Survival, as Assessed by the Independent Review Committee

PFS is established as a clinically relevant measure of treatment benefit and a correlate of OS in advanced melanoma, which in recent years has been an approvable endpoint in the setting of metastatic or unresectable melanoma for both targeted and immunotherapies (European Medicines Agency 2012). In a meta-analysis of 4416 metastatic melanoma patients, PFS was found to be a robust surrogate for OS in dacarbazine-controlled randomized trials of metastatic melanoma. Furthermore, PFS has also been demonstrated to be predictive of landmark OS for pembrolizumab (Robert et al. 2015a). In addition, owing to the increased number of active treatment options available and under investigation, resulting in patients receiving more lines of therapy than have previously been available, OS would likely be confounded by the use of effective subsequent-line therapies or by mortality unrelated to cancer (Flaherty et al. 2012).

Finally, full powering for OS requires large numbers of patients, and for this study, it would result in a significantly longer timeline, such that analysis of clinical benefit would not be available to patients with remaining unmet need and their physicians in a reasonable timeframe. As progression events provide reliable information on the treatment effect observed and generally are not confounded by subsequent lines of therapy, PFS provides a meaningful efficacy endpoint with earlier time to evaluation (Di Leo et al. 2003). In addition, 2-year landmark survival may provide a meaningful measure of benefit to patients and physicians.

In summary, multiple drugs, including both targeted therapy and immunotherapies, have been approved in metastatic melanoma in recent years on the basis of PFS, and extensive clinical experience validates PFS as a consistent strong correlate of survival across different treatment modalities.

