6.1 DETERMINATION OF SAMPLE SIZE

Approximately 450 patients will be randomized into the study.

The overall type I error (α) for this study is 0.05 (two-sided).

The type I error (α) for the analysis of the primary endpoint of IRC-assessed PFS is 0.01 (two-sided). The analysis of the primary endpoint of IRC-assessed PFS will take place when approximately 240 PFS events have occurred. Statistical considerations are based on the following assumptions:

- Stratified log-rank test at 0.01 significance level (two-sided)
- Median PFS of 5.5 months for the pembrolizumab arm
- Median PFS of 10.0 months for the cobimetinib plus atezolizumab arm

- Enrollment period of approximately 12 months
- Annual dropout rate of 5%
- No interim analysis for PFS

A total of 240 PFS events provides approximately 98% power to detect an improvement in median PFS from 5.5 months in the pembrolizumab arm to 10.0 months in the cobimetinib plus atezolizumab arm. This corresponds to a HR of 0.55, with a minimal detectable difference of 0.72. The PFS analysis will be conducted approximately 17 months after FPI.

The final analysis of the secondary endpoint of OS will be performed after the occurrence of approximately 295 deaths. A total of 295 deaths provides approximately 60% power to detect an improvement in median OS from 28 months in the pembrolizumab arm to 37.5 months in the cobimetinib plus atezolizumab arm, corresponding to an HR of 0.75, or 80% power to detect an HR of 0.70. Two interim analyses of OS will be conducted. The final OS analysis will be conducted approximately 68 months after FPI.

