6.9.2 Interim Efficacy Analyses of the Secondary Efficacy Endpoint

The study will incorporate three OS analyses (two interim analyses and one final analysis). The first OS interim analysis will be performed at the time of the primary PFS analysis when a projected number of 80 deaths are expected to have occurred. The second OS interim analysis will be performed after the occurrence of approximately 153 deaths and is projected to occur at approximately 28 months after the first patient is randomized. The final OS analysis will be performed after the occurrence of approximately 295 deaths and is projected to occur approximately 68 months after the first patient is randomized. The actual number of observed OS events at each interim analysis may differ from the estimates presented. The stopping boundaries are computed using Generalized Haybittle-Peto boundaries with unequal p-values of 0.001, 0.040, and 0.018 at the three OS analyses to control the overall type I error of the OS comparison at a two-sided 0.05 significance level. [Table 6](#) summarizes the assumptions and characteristics of the interim and final analyses for OS.

Table 6 Assumptions and Characteristics for the Interim and Final Analyses of Overall Survival

Assumptions	Findings
HR targeted	0.75
Targeted median (pembrolizumab)	28.0 months
Targeted median (cobimetinib + atezolizumab)	37.5 months
Projected enrollment period	12 months
First interim analysis (performed at the time of the PFS analysis)	
Estimated cutoff date ^a	17 months
Projected number of events (% of final events)	80 (27%)
Projected MDD ^b (p-value)	0.42 (<0.001)
Second interim analysis	
Estimated cutoff date ^a	28 months
Projected number of events (% of final events)	153 (52%)
Projected MDD ^b (p-value)	0.72 (<0.040)
Final analysis	
Estimated cutoff date ^a	68 months
Projected number of events (% of final events)	295 (100%)
Projected MDD ^b (p-value)	0.76 (<0.018)
Power	60%
α level (two-sided)	0.05

HR=hazard ratio; MDD=minimally detectable difference;
PFS=progression-free survival;

^a Estimated data cutoff time from first randomization. Analysis results will be available after data cleaning.

^b The largest observed HR that is projected to be statistically significant.

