2.4 ANALYSIS TIMING

The PFS primary analysis will be conducted when approximately 240 PFS events have occurred, which is expected to occur approximately 17 months after FPI. There is no planned interim analysis for PFS.

The study will incorporate three OS analyses (two interim analyses and one final analysis). The first OS interim analysis will be performed at the time of the primary PFS analysis when a projected number of 80 deaths are expected to have occurred. The second OS interim analysis will be performed after the occurrence of approximately 153 deaths and is projected to occur at approximately 28 months after the first patient is randomized. The final OS analysis will be performed after the occurrence of approximately 295 deaths and is projected to occur approximately 68 months after the first patient is randomized. Refer to Section 4.10 for the assumptions and characteristics of the interim and final analysis for OS.

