2.5 PREMATURE TERMINATION OF STUDY AFTER PRIMARY ANALYSIS

Given that the study did not meet the primary endpoint and did not demonstrate a benefit of cobimetinib plus atezolizumab vs. pembrolizumab, it will be terminated early. Therefore, the second interim and final OS analyses will not be conducted as specified elsewhere in this document. Instead, a final OS analysis will be conducted at the time of final database lock.

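### Should OS keep a formal test at 0.04 when PFS misses at 0.01, instead of being closed by the SAP's gate?

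*SAP*

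**What the plan says.** SAP 2.3 sets the study-wide two-sided error at 0.05 and tests PFS first at 0.01. If PFS succeeds, the key secondary endpoints are tested at 0.05 "in a hierarchical manner in the following order: OS, IRC-assessed objective response rate (ORR), and landmark OS". It gives no level for OS after a PFS miss.

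Protocol 6.1 declares the same 0.05 and says that the type I error "for the analysis of the primary endpoint of IRC-assessed PFS is 0.01 (two-sided"). Protocol 6.9.2 applies its Haybittle-Peto limits "at the three OS analyses to control the overall type I error of the OS comparison at a two-sided 0.05 significance level"; the nominal levels, in order, are 0.001, 0.040 and 0.018. Neither section makes OS conditional on PFS; nor does the synopsis or its copy in SAP Appendix 1. Section 6 of the Protocol sends the reader to the SAP for further detail.

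On precedence, SAP 1 states: "For purposes of registration, the analyses outlined in this SAP will supersede those specified in the protocol". SAP 4 repeats this for a regulatory filing.

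SAP 2.5 (version 3) records that PFS was not met and that the study will end early: "Therefore, the second interim and final OS analyses will not be conducted as specified elsewhere in this document". One OS analysis at final database lock takes their place.

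**The concern.** Two things look wrong.

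First, PFS takes 0.01 of the declared 0.05, and after a miss nothing takes the other 0.04. OS is the first key secondary endpoint, with three analyses and 295 deaths planned. An observed PFS HR above about 0.717 on 240 events rules out a formal OS claim. That includes HRs of 0.717 to 0.776, where the PFS p-value lies between 0.01 and 0.05.

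Second, someone with only the Protocol could expect OS to be tested at 0.05 whatever PFS shows. Added to 0.01 for PFS, that exceeds the declared 0.05.

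The alternative is a fallback fixed before the PFS analysis: OS at an overall 0.05 after a PFS success and at an overall 0.04 after a miss.

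**Working it through.** **Inputs.** PFS: 240 events, HR 0.55, two-sided 0.01, 1:1 allocation (SAP 2 and 2.3). OS: looks at 80, 153 and 295 deaths, projected at months 17, 28 and 68, nominal p-values 0.001/0.040/0.018 (SAP 4.10, Table 1). The documents give no correlation between the PFS statistic and the first OS look, so I assume a range of 0 to 0.5.

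**1. The plan's own figures.**
- PFS power = Φ(½√240 × |ln 0.55| − 2.576) = Φ(7.746 × 0.598 − 2.576) = Φ(2.055) = 98.0% (stated 98%).
- Largest significant PFS HR = exp(−2 × 2.576/√240) = 0.717 (stated 0.72). At p = 0.05 it is exp(−2 × 1.960/√240) = 0.776.
- OS, trivariate normal with correlation √(dᵢ/dⱼ) between looks: overall error 0.0503 (stated 0.05); power 60.2% at HR 0.75 (stated 60%) and 79.6% at HR 0.70 (stated 80%).

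**2. Familywise error for PFS and OS.**

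| Rule | Bound | Both nulls true (simulated) |
|---|---|---|
| SAP gate | 0.01 if PFS is null; 0.05 if only OS is null | 0.010 |
| Protocol read with no gate | 0.01 + 0.05 = 0.06 | 0.059–0.060 |
| Fallback | 0.01 + 0.04 = 0.05 | about 0.049 |

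The gate holds 0.05. The fallback does too, but needs its own boundary row: 0.001/0.030/0.016 gives an overall 0.0400. Keeping the present boundaries after a miss would give 0.01 + 0.0503 = 0.0603.

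**3. What the fallback gains.** PFS succeeds with probability 98.0%, 77.7%, 57.4% and 36.4% at HR 0.55, 0.65, 0.70 and 0.75. With zero correlation and both HRs at 0.75, the gate gives 0.364 × 0.602 = 21.9%. The fallback gives 0.219 + 0.636 × 0.576 = 58.5%. Over correlations 0 to 0.5, with follow-up to 295 deaths, the chance of a formal OS claim is:

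| PFS HR | OS HR | Gate | Fallback |
|---|---|---|---|
| 0.55 | 0.75 | 59–60% | 60% |
| 0.65 | 0.75 | 47–50% | 60% |
| 0.70 | 0.75 | 35–39% | 59% |
| 0.75 | 0.75 | 22–26% | 59% |
| 0.65 | 0.81 | 27–30% | 34% |
| 0.70 | 0.84 | 14–18% | 24% |
| 0.75 | 0.87 | 6–10% | 16–17% |

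The last three rows keep the design ratio of log hazard ratios, ln 0.75/ln 0.55 = 0.48, so that OS weakens along with PFS. This is my assumption. It is in keeping with Protocol 3.3.9, which treats PFS as a strong correlate of survival. Gains there are roughly 4 to 10 points.

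**4. Dependence on follow-up.** Take both HRs at 0.75 and suppose follow-up after a miss stops early, with the boundary reset to an overall 0.04. The fallback then gives 23–27% at 80 deaths, 46–47% at 153, 50–51% at 200 and 55% at 250, against 22–26% under the gate. Reaching 153 deaths takes 28 − 17 = 11 more months; reaching 295 takes 68 − 17 = 51.

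**5. The early-stopping rule.** Those early-stopping figures require that the last look is not chosen from OS data. Suppose 153 deaths could be declared final after seeing p < 0.0398, with follow-up otherwise continuing to 295 deaths at 0.016. OS error would then be 0.049 and the familywise error about 0.058.

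**The case for a change.** The best argument for a change is that a strict gate would hold 0.05 for PFS then OS even with PFS tested at 0.05. Testing PFS at 0.01 therefore buys nothing in familywise control unless the remaining 0.04 is spent elsewhere, and neither document says why it is not. The fallback leaves PFS power untouched, and OS power after a PFS success too. At PFS and OS HR 0.75, more than half the gain arrives by the second look, which "is projected to occur at approximately 28 months after the first patient is randomized".

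The arithmetic stands, and so does the point that the documents give no reason for the strict PFS level. Three things weaken the rest.

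- Protocol 3.3.9 explains why OS is not primary: "OS would likely be confounded by the use of effective subsequent-line therapies or by mortality unrelated to cancer", and full powering for OS would take much longer. That reasoning supports withholding an independent OS claim. The fallback also raises the chance of a false OS claim, when PFS HR is 0.75 and OS has no effect, from 0.018–0.020 to 0.044.
- The largest gains pair a much weaker PFS effect with an undiminished OS effect.
- They also need the sponsor to continue after a missed primary. Here it did not.

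On the mismatch, the Protocol is silent on a gate; it does not exclude one. PFS at 0.01, OS at 0.05 and a study-wide 0.05 fit together only under a hierarchy such as the one SAP 2.3 supplies. The figure near 0.06 comes from a reading that contradicts the Protocol's own 0.05.

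**Conclusion.** No change is needed. The gate controls the error for PFS and OS at the declared 0.05 and keeps OS in the secondary role that the Protocol argues for. The fallback is a legitimate alternative, but it is a trade-off. It gains about 1 point at the design PFS HR, roughly 4 to 10 points if OS weakens in proportion, and up to about 37 in the most favourable case shown. In return it brings a higher chance of a false OS claim and 11 to 51 months of follow-up after a miss. It also had to be fixed before the PFS analysis, and SAP version 3 follows the miss.

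The Protocol's silence is missing detail that the SAP fills and, for registration, overrides. Nor does the OS analysis at database lock carry a formal claim: under SAP 2.3 it is descriptive. The OS hazard ratio, confidence interval and Kaplan-Meier estimates in SAP 4.4.2.1 are still reported. Saying this outright in Protocol 6.1 and 6.9.2 and in SAP 2.5 and 4.10 would be tidy, but would not alter any analysis.

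The sizes rest on normal approximations at the planned event counts, proportional hazards, and a PFS–OS correlation of 0 to 0.5. The error check covers PFS and OS, not the later ORR and landmark OS tests.
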